### **3. STUDY OBJECTIVES AND ENDPOINTS**

#### **3.1. Study Objectives**

##### **3.1.1. Primary**

- Assessment of the safety, tolerability, and reactogenicity of one dose of ChAd155-RG at  $5 \times 10^{10}$  vp per dose, or one or two doses of ChAd155-RG at  $1 \times 10^{11}$  vp per dose.
- Comparison of the safety, tolerability, and reactogenicity of one or two doses of ChAd155-RG, with three doses of RABAVERT.

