#### 8.2.1. Rabies Virus Neutralizing Antibodies (VNA)

Results from the RFFIT assay will be reported in IU/mL, with a typical range of 1-15 IU/mL. Results beyond 15 IU/mL will require dilution and retesting. The lower limit of quantification for the RFFIT assay is 0.1 IU/mL; values below the LLOQ will be imputed as 1/2 the LLOQ, or 0.05 IU/mL.

Serum samples for rabies VNA will be collected prior to vaccination (Day 1) and on Day 8, Day 15, Day 22, Day 29, Day 91, Day 181, and Day 381.

For each sample time point (and peak post-vaccination value), the GMT and 95% CI of the rabies VNA results will be analyzed and presented as described above, including post-baseline seroconversion rates and exact Clopper-Pearson 95% CI for the mITT and PP populations ([Table 21](#) and [Table 22](#), respectively).

Graphical displays of the reverse cumulative distribution curves, by time point and vaccine group, will be presented for the mITT and PP populations ([Figure 2](#) and [Figure 3](#), respectively). Similarly, graphical box-and-whisker plots will be presented for rabies VNA titers ([Figure 4](#) and [Figure 5](#), respectively) and for the percent seroconversion rate and 95% CIs ([Figure 6](#) and [Figure 7](#), respectively).

The pair-wise differences in seroconversion rates will be computed at each post-vaccination visit, with corresponding 95% CI computed via the Miettinen and Nurminen score method, for the mITT and PP populations ([Table 23](#) and [Table 24](#), respectively). Pair-wise differences and 95% CIs will be based on standard 2 x 2 table analyses and estimated using PROC FREQ and the RISKDIFF option in SAS. See pseudo code below.

```
PROC FREQ DATA=aa;
  TABLE Grp*Response / RISKDIFF(CLTYPE=MN);
```

*OUTPUT OUT=bb RISKDIFF;  
RUN;*

A listing of all rabies VNA titers will be presented in [Listing 9](#).

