### 9.3.1. **Solicited Events and Symptoms**

Solicited local and systemic adverse events were collected prior to each vaccination, 30 minutes post-vaccination and through 7 days after each vaccination. Systemic events include: feverishness, fatigue, malaise, myalgia, arthralgia, headache, nausea, and fever (based on temperature). Local injection site events include: pain, tenderness, pruritis, ecchymosis (grade and measurement), erythema (grade and measurement) and induration (grade and measurement). See [Table 7](#), [Table 8](#), [Table 9](#), and [Table 10](#) for grading details. Each solicited AE will be summarized separately for each vaccination and over all vaccinations, by vaccination group. For ecchymosis, erythema, and induration, the severity based on measurement will be presented separately.

The proportion of subjects (and exact 95% CI) reporting at least one solicited AE over each post-vaccination follow-up period will be summarized for each solicited AE, any systemic symptom, any local symptom, and any symptoms ([Table 31](#), [Table 32](#), [Table 33](#), [Table 34](#), and [Table 35](#)). The 95% CI will be calculated using Clopper-Pearson methodology from a binomial distribution (SAS Proc Freq with a binomial option).

Solicited local injection site and systemic AEs will also be summarized by symptom, dose group, severity, and individual time point (pre-dose, 30 mins post-dose, days 1 to 8). These results will be displayed by dose and dose group in [Table 36](#) through [Table 65](#).

Bar graphs representing the percent of subjects with solicited systemic AEs by dose group, post-vaccination time point, and maximum severity will be presented in [Figure 10](#), [Figure 11](#), [Figure 12](#), [Figure 13](#), and [Figure 14](#). Similar graphs will be presented for solicited local AEs in [Figure 15](#), [Figure 16](#), [Figure 17](#), [Figure 18](#), and [Figure 19](#).

Solicited AEs by subject will be presented in [Listing 11](#) (systemic symptom) and [Listing 12](#) (local symptom).

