## 9.1 Overall Study Design and Plan Description

**Table 1: Study Design**

Study Group	N	Vaccine	Dosage of Vaccine	Number of Vaccine Doses	Schedule of Vaccine and Placebo Injections	Route	Description of Study Group
A	14 including 3 sentinels #	ChAd155-RG	5x10  vp*	1	Day 1 vaccine; Days 8, 15, and 22 placebo	IM	Lower dosage, 1 dose
B	14 including 3 sentinels	ChAd155-RG	1x10  vp	1	Day 1 vaccine; Days 8, 15, and 22 placebo	IM	Higher dosage, 1 dose
C	10	ChAd155-RG	1x10  vp	2	Days 1 and 15 vaccine; Days 8 and 22 placebo	IM	Higher dosage, 2 doses
D	12 including 2 sentinels	RABAVERT	1 mL	3	Days 1, 8, and 22 vaccine; Day 15 placebo	IM	Active comparator (licensed vaccine)

\*Abbreviations: vp, viral particles; IM, intramuscular

#Groups A, B and D each include sentinel subjects as indicated. Note: Two of the sentinels will receive a three-dose series of RABAVERT. To maintain blinding, the other sentinels will receive placebo injections on Days 8, 15, and 22 as indicated in the table.

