Fever												
Any Local Symptom												
Pain												
Tenderness												
Pruritis												
Ecchymosis Grade												
Ecchymosis Measurement												
Erythema Grade												
Erythema Measurement												
Induration Grade												
Induration Measurement												
Note: N = Number of subjects in the Safety Population who received the specified dose; n = Number of subjects reporting event. Severity is the maximum severity reported over all solicited symptoms post dosing for each subject. a Low dose, and both high dose combined.												

**Table 35: Number and Percentage of Subjects Experiencing Solicited Adverse Events by Symptom, Maximum Severity, Dose, and Vaccination Group - Post Any Dose**

Symptom/ Severity	Low Dose ChAd155- RG (N=X)		High Dose ChAd155- RG (x1) (N=X)		High Dose ChAd155- RG (x2) (N=X)		RABAVERT (N=X)		All Subjects (N=X)	
	n (%)	95% CI	n (%)	95% CI	n (%)	95% CI	n (%)	95% CI	n (%)	95% CI
Any Symptom										
Any Severity	x (xx)	xx, xx	x (xx)	xx, xx	x (xx)	xx, xx	x (xx)	xx, xx	x (xx)	xx, xx
None										
Mild										
Moderate										
Severe										
Repeat for:										
Any Systemic Symptom										
Feverishness										
Fatigue										
Malaise										
Myalgia										
Arthralgia										
Nausea										
Headache										
Fever										
Any Local Symptom										
Pain										
Tenderness										
Pruritis										
Ecchymosis Grade										
Ecchymosis Measurement										
Erythema Grade										
Erythema Measurement										
Induration Grade										
Induration Measurement										
Note: N = Number of subjects in the Safety Population who received the specified dose; n = Number of subjects reporting event.										
Severity is the maximum severity reported over all solicited symptoms post dosing for each subject.										

**Table 36: Number and Percentage of Subjects Experiencing Any Solicited Adverse Event by Maximum Severity and Day Post Dosing - Low Dose ChAd155-RG, Dose 1\***

Treatment Received = ChAd155-RG (N = X)												
	Severity	Pre-Dose (N*=X)	30 Mins. Post-Dose (N*=X)	Day 1 a (N*=X)	Day 2 (N*=X)	Day 3 (N*=X)	Day 4 (N*=X)	Day 5 (N*=X)	Day 6 (N*=X)	Day 7 (N*=X)	Day 8 (N*=X)	
		n (%)	n (%)	n (%)	n (%)	n (%)	n (%)	n (%)	n (%)	n (%)	n (%)	
Any Solicited Symptom	Any Severity	x (xx)	x (xx)	x (xx)	x (xx)	x (xx)	x (xx)	x (xx)	x (xx)	x (xx)	x (xx)	
	None											
	Mild											
	Moderate											

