**Table 57:** **Number and Percentage of Subjects Experiencing Any Solicited Adverse Event by Maximum Severity and Day Post Dosing – RABAVERT, Dose 3\***

**Table 58:** **Number and Percentage of Subjects Experiencing Any Solicited Adverse Event by Maximum Severity and Day Post Dosing – RABAVERT, Dose 4\***

**Table 59:** **Number and Percentage of Subjects Experiencing Any Solicited Adverse Event by Maximum Severity and Day Post Dosing – RABAVERT, Dose 1, 2, 4\***

[Implementation note: The maximum severity of each symptom reported by each subject each day over all specified doses is reported.]

**Table 60:** **Number and Percentage of Subjects Experiencing Any Solicited Adverse Event by Maximum Severity and Day Post Dosing – RABAVERT, Any Dose\***

[Implementation note: The maximum severity of each symptom reported by each subject each day over all specified doses is reported.]

**Table 61:** **Number and Percentage of Subjects Experiencing Any Solicited Adverse Event by Maximum Severity and Day Post Dosing - All Subjects, Dose 1\***

**Table 62:** **Number and Percentage of Subjects Experiencing Any Solicited Adverse Event by Maximum Severity and Day Post Dosing - All Subjects, Dose 2\***

**Table 63:** **Number and Percentage of Subjects Experiencing Any Solicited Adverse Event by Maximum Severity and Day Post Dosing - All Subjects, Dose 3\***

**Table 64:** **Number and Percentage of Subjects Experiencing Any Solicited Adverse Event by Maximum Severity and Day Post Dosing - All Subjects, Dose 4\***

**Table 65:** **Number and Percentage of Subjects Experiencing Any Solicited Adverse Event by Maximum Severity and Day Post Dosing - All Subjects, Any Dose\***

[Implementation note: The maximum severity of each symptom reported by each subject each day over all specified doses is reported.]

**14.3.1.2 Unsolicited Adverse Events****Table 66: Number and Percentage of Subjects Experiencing Unsolicited Adverse Events Post-Dose 1 and Prior to Dose 2 by MedDRA System Organ Class, Preferred Term, and Severity - Safety Population\***

[Implementation Note: For preliminary analyses, data will be reported through the data cut-off date.]

MedDRA Classification	Severity	Low Dose ChAd155-RG (N=X)			High Dose ChAd155-RG (x1) (N=X)			High Dose ChAd155-RG (x2) (N=X)			Combined High Dose ChAd155-RG (N=X)			RABAVERT (N=X)			All Subjects (N=X)		

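### The second primary objective compares ChAd155-RG with RABAVERT, but the SAP plans no between-arm safety estimate, and its all-injection table (Table 35) mixes active and saline injections without a pooled active-dose counterpart for Groups C and D

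*SAP*

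**What the plan says.** SAP section 3.1.1 gives as the second primary objective: "Comparison of the safety, tolerability, and reactogenicity of one or two doses of ChAd155-RG, with three doses of RABAVERT".

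For solicited events, SAP section 9.3.1 states: "Each solicited AE will be summarized separately for each vaccination and over all vaccinations, by vaccination group". The intervals there are Clopper-Pearson intervals on each group's own proportion. Protocol section 11.4.3 asks for the same two kinds of summary with exact intervals.

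The outputs in SAP Appendix 1 are:

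- Tables 31 to 34 give solicited events after Doses 1, 2, 3 and 4 with intervals. In Tables 32 to 34 the saline columns are headed as placebo.
- Table 35, by "Maximum Severity, Dose, and Vaccination Group - Post Any Dose", covers all four injections, with columns headed by vaccination group.
- Tables 36 to 65 are by-day displays without intervals. One of them, Table 59, pools the active RABAVERT injections ("RABAVERT, Dose 1, 2, 4").

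For seroconversion, SAP section 8.2.1 plans pairwise differences with "95% CI computed via the Miettinen and Nurminen score method". No safety section contains an equivalent.

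**The concern.** A comparative primary objective has no comparative estimate attached to it. The reader must set one group's exact interval beside another's and judge by eye, while a secondary endpoint gets a formal difference with an interval.

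The table most likely to be used for that visual comparison is Table 35, because it alone gives intervals over the whole regimen. Its columns carry the vaccine names, but more than half of the planned injections behind them are saline, in unequal numbers by arm. Nothing on the table says so. Protocol section 9.2.1 also treats every solicited injection-site event as related, with no exception for saline. At stake is whether a real difference in reactogenicity can be seen, and whether readers know which quantity they are looking at.

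**Working it through.** **Injection counts.** SAP Table 1 gives the schedules: "Day 1 vaccine; Days 8, 15, and 22 placebo" for Groups A and B, "Days 1 and 15 vaccine; Days 8 and 22 placebo" for C and "Days 1, 8, and 22 vaccine; Day 15 placebo" for D.

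| Group | N | Active | Saline |
|---|---|---|---|
| A | 14 | 1 | 3 |
| B | 14 | 1 | 3 |
| C | 10 | 2 | 2 |
| D | 12 | 3 | 1 |

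Saline injections total 14×3 + 14×3 + 10×2 + 12×1 = 116 of 50×4 = 200, or 58%.

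**The plan's own figures.** The documents give no precision or power for a between-arm safety comparison. Their within-group figures reproduce. For example, the SAP Table 4 detectable rate for N = 14 and power 0.80 is 1 - (1 - 0.80)^(1/14) = 10.9%, as stated.

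**Target 1: vaccine-attributable risk over the regimen.** Let V be the probability of a vaccine-attributable symptom over the whole regimen, and b the background probability in each injection window, active or saline, with independence. Table 35 then estimates

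1 - (1 - b)^4 (1 - V)

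in every arm. If V is equal in A and D, the table shows equal rates: at V = 50% and b = 20%, 1 - 0.8^4 × 0.5 = 79.5% in both. If V differs, the displayed difference is (1 - b)^4 times the true one:

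- b = 5.3%: 0.947^4 = 0.80, so 10 true points appear as about 8.
- b = 20%: 0.8^4 = 0.41, so 10 true points appear as about 4.

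The 5.3% is the only saline rate in the documents: placebo injection-site pain in the earlier ChAd155 RSV trial (protocol section 2.3.1). The 20% is an assumption.

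**Target 2: risk after active injections only.** Let this total risk be R in every arm, and q the saline risk per injection. Table 35 shows 1 - (1 - R)(1 - q)^3 for A and B and 1 - (1 - R)(1 - q) for D. At an assumed R = 50%:

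| q | A, B | D | Gap (points) |
|---|---|---|---|
| 5.3% | 57.5% | 52.6% | +4.9 |
| 10% | 63.5% | 55.0% | +8.5 |
| 20% | 74.4% | 60.0% | +14.4 |
| 30% | 82.8% | 65.0% | +17.8 |

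The gap shrinks as R rises: at R = 90% it is 1.0 to 3.6 points over the same q, and at R = 100% it is zero.

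**What a pooled active-dose table would do.** It has one window in A and B, two in C and three in D. Under target 1 with V = 50% and b = 20%, A shows 1 - 0.8 × 0.5 = 60.0% and D shows 1 - 0.8^3 × 0.5 = 74.4%. That is a spurious 14.4 points against RABAVERT.

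**What exists already.** Table 31 is active product in every arm, and for A and B it is the complete active exposure. Tables 32 and 34 give the later RABAVERT doses, and Table 33 gives the second ChAd155-RG dose. The proportion of Group C or D subjects reacting to any active dose cannot be recovered from these, because it needs subject-level counts across doses. Table 59 supplies that pooling for RABAVERT only, by day and without intervals. Nothing pools Doses 1 and 3 for Group C.

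**Precision of a difference.** For illustrative counts of 10/14 versus 6/12, the difference is 71.4% - 50.0% = +21.4 points, with a Miettinen-Nurminen 95% CI of -16.6 to 54.4.

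**The case against.** A reader might infer that Table 35 counts saline symptoms as vaccine reactions and so makes ChAd155-RG look more reactogenic than RABAVERT when it is not. The documents do not support this as a general statement. All subjects receive four injections on one schedule, so background symptoms have the same number of opportunities in each arm. The gap against A and B arises only under target 2, which fixes the same total risk over one active window in A and three in D. If each active dose carried the same 50% risk, Table 35 would place A below D, by 8.4 points (q = 30%) to 30.6 points (q = 5.3%). The one documented saline rate, 5.3% for pain, comes with 100% pain in vaccine recipients. If that carried over, saline could not inflate pain in the ChAd155-RG arms at all.

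A reader might also infer that no active-dose results are planned. That is wrong: Tables 31 to 34 provide them dose by dose with intervals, and they label the saline columns.

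It can further be said that Table 35 follows the protocol, that protocol section 11.1 calls the trial exploratory with no formal hypothesis test, and that intervals at these sample sizes are too wide to settle much. All of this stands. It removes any charge of error or of bias in one fixed direction. It does not explain why the comparative primary objective lacks an estimate that the secondary endpoint has. Wide uncertainty is a reason to display an interval for the difference.

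**Conclusion.** The point holds as a gap in the planned outputs. No safety endpoint has a between-arm estimate, although the second primary objective is a comparison. Table 35 mixes 3, 3, 2 and 1 saline injections per subject with the active doses and does not say so. No pooled active-dose table exists for Group C, and none with intervals exists for C or D.

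For vaccine-attributable risk, Table 35 is fair between arms but muted: differences shrink to about 80% at b = 5.3% and 41% at b = 20%. It overstates A and B against D only if the target is risk after active injections alone. The sizes rest on assumed background or saline rates, on independence between windows, and on subjects receiving all four injections. Unequal discontinuation would upset the balance. Neither Table 35 nor a pooled active-dose table is sufficient alone, and the SAP should state which quantity each one addresses.

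**What to change.** 1. Add Miettinen-Nurminen differences with 95% CIs for each ChAd155-RG group versus RABAVERT, for any symptom, any local symptom, any systemic symptom and Grade 2 or higher. Do this for Table 35 (whole regimen, four windows per arm) and Table 31 (Dose 1, one active window per arm). Note that Table 31 compares first doses and not full regimens for C and D.
2. Add a supplementary table in the Table 35 layout, covering any active dose, with exact CIs: Dose 1 for A and B, Doses 1 and 3 for C, Doses 1, 2 and 4 for D. Add a footnote that the arms contribute 1, 1, 2 and 3 windows, so background symptoms count more against RABAVERT. It should not be the sole analysis for the second primary objective.
3. Footnote Table 35 with the number of active and saline injections per arm.

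The cost is one extra table, a few added rows and footnotes, using a method the SAP already specifies. No data collection, design or sample size changes. The differences will be imprecise and should be presented as descriptive.

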### 14.3.2 Listing of Deaths, Other Serious and Significant Adverse Events

**Table 76: Listing of Serious Adverse Events\***

[Implementation Note: For preliminary analyses, data will be reported through the data cut-off date.]

Adverse Event	Associated with Dose No.	No. of Days Post Associated Dose (Duration)	No. of Days Post Dose the Event Became Serious	Reason Reported as an SAE	Severity	Relationship to Study Treatment	If Not Related, Alternative Etiology	Action Taken with Study Treatment	Subject Discontinued Due to AE	Outcome	MedDRA System Organ Class	MedDRA Preferred Term
Subject ID: , Vaccination Group: , AE Number:												
Comments:												
Subject ID: , Vaccination Group: , AE Number:												
Comments:												

**Table 77: Listing of Non-Serious, Unsolicited, Moderate or Severe Adverse Events\***

[Implementation Note: For preliminary analyses, data will be reported through the data cut-off date.]

Adverse Event	Associated with Dose No.	No. of Days Post Associated Dose (Duration)	Severity	Relationship to Study Treatment	If Not Related, Alternative Etiology	Action Taken with Study Treatment	Subject Discontinued Due to AE	Outcome	MedDRA System Organ Class	MedDRA Preferred Term
Subject ID: , Vaccination Group: , AE Number:										
Comments:										
Subject ID: , Vaccination Group: , AE Number:										
Comments:										

**Table 78: Listing of Other Significant Adverse Events\***

[Implementation Note: For preliminary analyses, data will be reported through the data cut-off date. Events will include, but are not limited to, AEs leading to subject withdrawal, study drug interruption or discontinuation, and new onset chronic medical conditions.]

Adverse Event	Number of Doses Received at Time of Event	No. of Days Post Associated Dose	Duration of Event	Severity	MedDRA System Organ Class	NOCMC?	Relationship	Outcome
Subject ID: , Vaccination Group: , AE Number:								
Comments:								
Subject ID: , Vaccination Group: , AE Number:								
Comments:								

**14.3.4 Abnormal Laboratory Value Listings (by Subject)****Table 79: Listing of Abnormal Laboratory Results of Grade 1 or Greater – Chemistry\***

Subject ID	Vaccination Group	Sex	Age (Years)	Planned Time Point	Actual Study Day	Laboratory Parameter (Units)	Result (Severity)	Relationship to Treatment	If Not Related, Alternate Etiology	Action Taken with Study Treatment	Subject Discontinued Due to Result?

Table with similar format:

**Table 80: Listing of Abnormal Laboratory Results of Grade 1 or Greater – Hematology\***

### 14.3.5 Displays of Laboratory Results

#### 14.3.5.1 Chemistry Results

**Table 81: Abnormal Laboratory Results by Maximum Severity, Time Point, and Vaccination Group - Any Chemistry Parameter\***

Time Point	Vaccination Group	N	None		Mild/ Grade 1		Moderate/ Grade 2		Severe/ Grade 3		Any Severity	
			n (%)	95% CI	n (%)	95% CI	n (%)	95% CI	n (%)	95% CI	n (%)	95% CI
Baseline (Pre-Dose 1)	Low Dose ChAd155-RG	x	x (xx)	(xx, xx)	x (xx)	(xx, xx)	x (xx)	(xx, xx)	x (xx)	(xx, xx)	x (xx)	(xx, xx)
	High Dose ChAd155-RG (x1)											
	High Dose ChAd155-RG (x2)											
	Combined High Dose a ChAd155-RG											
	RABAVERT											
	Total											
Repeat for:												
Day 2 (1 Day Post Dose 1)												
Day 8 (Pre-Dose 2)												
Day 16 (2 Days Post Dose 3)												
Day 22 (Pre-Dose 4)												
Max Severity Post Baseline												

Note: The “Max Post Baseline” rows indicate the maximum severity of abnormal laboratory results experienced by each subject at any time point post baseline, including unscheduled assessments.  
N = Number of subjects in the Safety Population; n = number of subjects with laboratory values in the respective category.  
a Both high dose groups combined.

Tables with similar format:

---

